6.1.2 Delayed Yoga Group (DYG) Schedule of Evaluations

Assessment	V1	V2	V3	V4	V5	V6***	V7	V8	V9	V10	V11	V12
Informed Consent Form	X											
Demographics/Contact Information	X											
Clinician-Administered Psychiatric History Form	X											
Inclusion/Exclusion Criteria	X											
Safety Labs (collected by research coordinator)	X											
1. Blood												
2. ECG												
3. Urine drug screen												
4. Urine pregnancy test (Female)												
Medical History	X											
Physical Examination by DCRP psychiatrist	X					X				X	X	
Habits Questionnaire	X					X				X	X	
MINI	X											
C-SSRS (lifetime and past year V1; since last visit all other visits)	X				X	X				X	X	X
Reproductive Status Questionnaire (Female)	X											
IDS-CR	X	X	X	X	X	X	X	X	X	X	X	X
HAM-D-28		X				X	X				X	X
Self-Rated Questionnaires: STAI; SF-36; Q-LES-Q; EIFI; PSS; PSQI; FFMQ; RRS	X	X	X	X	X	X	X	X	X	X	X	X
URICA		X				X	X				X	
Concomitant Medications	X	X	X	X	X	X	X	X	X	X	X	X
Vital Signs by research coordinator	X	X	X ⁺	X ⁺	X	X	X	X ⁺	X ⁺	X	X	X
Randomization		After baseline visit										
Psychoeducational Session		X					X					

Waist-to-Hip Ratio measured by research coordinator		X			X	X	X			X	X	X
Physiological Markers 1. Inflammatory markers (blood) 2. Cortisol (salivary)*		X			X	X	X**			X	X	X
Sleep Diary		X			X	X	X			X	X	X
Adverse Events		X	X	X	X	X	X	X	X	X	X	X
Hot Yoga Beliefs Scale		X				X	X				X	X
Acceptability Interview											X	
MINI Mood Module						X					X	X
QIDS-C and Weekly Phone Monitoring Form	<hr/> > On weeks in between V2-V3, V3-V4, V4-V5, V5-V6, V6-V7, V7-V8, V8-V9, V9-V10, V10-V11, V11-V12											
Pre- and Post-Yoga Scales over the STAI State, EIFI)	30 minutes prior to and 30 minutes post each yoga class											

6.2 Description of Evaluations

Figures 6.1.1 and 6.1.2 above outline a detailed description of evaluation visits. Additional information not included in this figure is listed below.

6.2.1 Screening Evaluation

Consenting Procedure

Prior to engaging in any study related activities, informed consent will be obtained by an MD- or PhD-level clinician or supervised psychology intern at the DCRP. One informed consent will be obtained for the screening and study procedures. Patients will be informed during the consent process that their participation is voluntary and their relationship with their prescribing physician will be unaffected by any choice to discontinue study participation. All participants will be informed that they can decline to answer any questions that they find upsetting and may withdraw from study participation at any time. The consent form will include the study procedures, information about potential risks and benefits of participation, and information regarding who they can contact with further questions or concerns. Patients will be alerted to the nature of the hyperthermic yoga practice during the consent process. Participants will have 24-hour pager access to an internal medicine physician, [name], whose specialty is in alternative medicine. This information will be given in the consent form. Documentation of informed consent will be kept in the Documentation of the Informed Consent Process for Onsite Subject File.

Visit 1: Screen – IYG and DYG

The screening visit will last approximately 3 hours. The purpose of this visit is to determine study eligibility. The two Figures above (6.1.1 and 6.1.2) outline the procedures for the screening visit, which are the same for the IYG and DYG. All of the screening items will be completed prior to the baseline visit (within 21 days of the screening visit).

- Informed Consent Form
- Demographics/Contact Information
- Clinician-Administered Psychiatric History Form
- Inclusion/Exclusion Criteria
- Safety Labs (i.e., blood, ECG, urine drug screen, urine pregnancy test [female] collected by a trained research coordinator)
 - Blood draw: A phlebotomy trained research coordinator at the DCRP will draw 11mL of blood (one 8mL tiger top tube and one 3mL lavender top tube).
- Medical History
- Physical Examination conducted by DCRP psychiatrist
- Habits Questionnaire
- MINI
- C-SSRS Lifetime and Past Year
- Reproductive Status Questionnaire (female)
- IDS-CR
- Self-Rated Questionnaires: STAI, SF-36, Q-LES-Q, EIFI, PSS, PSQI, FFMQ, RRS
- Concomitant Medications

- Vital signs
- Give salivettes and instructions to bring back salivary cortisol samples to their baseline visit
- Give Sleep Diary

6.2.2 Enrollment, Baseline, and/or Randomization

Enrollment

Enrollment is defined as the date all of the screening criteria are met— occurring between screening (visit 1) and baseline (visit 2).

Baseline Assessments (Visit 2 for IYG; Visits 2 and 7 for DYG)

At this visit subjects will meet with a study clinician for a 50-minute psychoeducational (see First Heated Yoga Class: What to Expect) and motivational session. Subjects will be asked to discuss reasons for wanting to try the hyperthermic yoga and also to discuss potential barriers to participation.

Visit 2: Baseline - IYG and DYG

- IDS-CR
- HAM-D-28
- Self-Rated Questionnaires: STAI, SF-36, Q-LES-Q, EIFI, PSS, PSQI, FFMQ, RRS, URICA
- Concomitant Medications
- Vital Signs
- Psychoeducational Session
- Waist-to-Hip Ratio
- Physiological Markers (i.e., inflammatory markers [blood], cortisol [saliva])
 - Please see section 9.5.2 for details
- Collect Sleep Diary (can bring to the following visit as long as it was completed for the right week)
- Collect salivates (can bring to the following visit as long as it was collected at the right time period)
- Adverse Events
- Hot Yoga Beliefs Scale

Visit 7: Repeat Baseline - DYG

- IDS-CR
- HAM-D-28
- Self-Rated Questionnaires: STAI, SF-36, Q-LES-Q, EIFI, PSS, PSQI, FFMQ, RRS, URICA
- Concomitant Medications
- Vital Signs
- Psychoeducational Session (refresher)
- Waist-to-Hip Ratio
- Physiological Markers[^] (i.e., inflammatory markers [blood], cortisol [saliva])
- Collect Sleep Diary (can bring to the following visit as long as it was completed for the right week)
- Adverse Events

- Hot Yoga Beliefs Scale

[^]If this visit takes place within 14 days of Visit 6, Physiological Markers will not be repeated at this visit.

At the end of the Baseline Visit that occurs before they start the yoga (V2 or V7), participants will be handed a packet of self-rated questionnaires (i.e. STAI-State and EIFI) to complete within 30 minutes prior and 30 minutes post each yoga class they attend. We will ask participants to note time and date on the top of each form. These questionnaires will provide data on acute mood changes pre- and post-yoga. [name] co-mentor [name] uses these questionnaires to gather the same data in her RO1 (5R01AT007483-05). Including this will allow us to compare data across studies.

Participants will also be handed a "Yoga Information" form at the end of the Baseline Visit that occurs before they start the yoga (V2 or V7), which will provide information about the studio locations and the class logistics.

Pre- and Post-Yoga Classes Scales – IYG and DYG

- Self-Rated Questionnaires (STAI-State only, EIFI)

Randomization

Patients will be randomized prior to visit 3, assessment visit 1. Research Coordinators will conduct the randomization and will inform [name] and participants of which group they have been randomized to at the end of their Baseline Visit, once all measures have been completed.

6.2.3 Blinding

The study clinician-assessors will be blinded. The research assistant welcoming the subject will remind the subject not to unblind the assessors at each assessment visit. Blinded assessors will complete all primary and secondary endpoint collection.

The randomization scheme will be executed by our biostatistician who will be blinded to treatment assignment and will also have no influence on outcome assessments. Our biostatistician will establish the blind and deliver it to the designated research assistant for this study. The Principal Investigator (PI) will not be blinded, since the PI will be delivering the psychoeducation preparatory visit (pre-yoga start) and also will be performing the bi-weekly phone monitoring. The PI will not have access to the data until the study database is locked. The DSMB identified in the submission will have access to unblinded data and will monitor adverse and serious adverse events.

Breaking the Blind: the PI, [name], and Medical Monitor, [name], are both unblinded to the intervention arm of each subject. In the event of a medical AE/SAE, [name] or his designee will be responsible for assuring safety of the patient. In the event of a psychiatric AE/SAE, [name] or her designee will be responsible for assuring the safety of the patient.

6.2.4 Follow-up Visits

Phone visits will occur bi-weekly from baseline through the end of the study intervention period. During the 1 month follow-up period, there will be a phone call during the midpoint (2-weeks into the follow-up period).

Assessment visits will be completed within a reasonable time frame (+/- 3 workday window), but may occur outside this window if deemed appropriate by study staff.

Visit 3 (Week-1 Assessment)* – IYG and DYG

- IDS-CR
- Self-Rated Questionnaires: STAI, SF-36, Q-LES-Q, EIFI, PSS, PSQI, FFMQ, RRS
- Concomitant Medications
- Vital Signs⁺
- Adverse events

Visit 4 (Week-3 Assessment)* – IYG and DYG

- IDS-CR
- Self-Rated Questionnaires: STAI, SF-36, Q-LES-Q, EIFI, PSS, PSQI, FFMQ, RRS
- Concomitant Medications
- Vital Signs⁺
- Give salivettes
- Give Sleep Diary (can bring to the following visit as long as it was completed for the right week)
- Adverse Events

Visit 5 (Week-5 Assessment) – IYG and DYG

- C-SSRS since Last Visit
- IDS-CR
- Self-Rated Questionnaires: STAI, SF-36, Q-LES-Q, EIFI, PSS, PSQI, FFMQ, RRS
- Concomitant Medications
- Vital Signs
- Waist-to-Hip Ratio
- Physiological Markers (i.e., inflammatory markers [blood], cortisol [saliva])
- Give salivettes
- Collect and give Sleep Diary (can bring to the following visit as long as it was completed for the right week)
- Adverse Events

Visit 8 (Week-1 Yoga Assessment) – DYG

- IDS-CR
- Self-Rated Questionnaires: STAI, SF-36, Q-LES-Q, EIFI, PSS, PSQI, FFMQ, RRS
- Concomitant Medications
- Vital Signs⁺
- Adverse Events

Visit 9 (Week-3 Yoga Assessment) – DYG

- IDS-CR
- Self-Rated Questionnaires: STAI, SF-36, Q-LES-Q, EIFI, PSS, PSQI, FFMQ, RRS
- Concomitant Medications
- Vital Signs⁺
- Give salivettes
- Give Sleep Diary
- Adverse Events

Visit 10 (Week-5 Yoga Assessment) – DYG

- C-SSRS since Last Visit
- IDS-CR
- Self-Rated Questionnaires: STAI, SF-36, Q-LES-Q, EIFI, PSS, PSQI, FFMQ, RRS
- Concomitant Medications
- Vital Signs
- Waist-to-Hip Ratio
- Physiological Markers (i.e., inflammatory markers [blood], cortisol [saliva])
- Give salivettes
- Collect and give Sleep Diary (can bring to the following visit as long as it was completed for the right week)
- Adverse Events

⁺Note that assessment visits will in most cases take place in person, however may take place over the phone in extenuating circumstances to reduce subject burden or accommodate subject schedules. In these cases, visits may be split into two separate occasions within the appropriate window with clinician-rated measures taking place by phone if needed. If assessment visits 3, 4, 8, and 9 take place by phone, no vital signs will be obtained. For all other visits blood is required for either safety procedures or outcome data.

6.2.5 Completion/Final Evaluation

Visit 6: Study Primary Endpoint (Week-8) for IYG and DYG (repeated for DYG in Visit 11 as 9-week Yoga Assessment)/Early Discontinuation Visit – IYG and DYG

- Physical Examination
- Habits Questionnaire
- C-SSRS since Last Visit
- IDS-CR
- HAM-D-28
- Self-Sated Questionnaires (STAI, SF-36, Q-LES-Q, EIFI, PSS, PSQI, FFMQ, RRS, URICA)
- Concomitant Medications
- Vital Signs
- Waist-to-Hip Ratio
- Physiological Markers (i.e., inflammatory markers [blood], cortisol [saliva])

- Collect Sleep Diary (can bring to the following visit as long as it was completed for the right week)
- Adverse Events
- Hot Yoga Beliefs Scale
- Acceptability Interview (completed at Visit 11 for DYG)
- MINI Mood Module

Final Evaluation: 1-Month Follow-Up Post-Yoga Visit – IYG (Visit 7) and DYG (Visit 12)

- Physical Examination
- Habits Questionnaire
- C-SSRS since Last Visit
- IDS-CR
- HAM-D-28
- Self-Rated Questionnaires (STAI, SF-36, Q-LES-Q, EIFI, PSS, PSQI, FFMQ, RRS)
- Concomitant Medications
- Vital Signs
- Waist-to-Hip Ratio
- Physiological Markers (i.e., inflammatory markers [blood], cortisol [saliva])
- Collect Sleep Diary
- Adverse Events
- Hot Yoga Beliefs Scale
- MINI Mood Module

Potential Reasons for Early Termination

Subjects can be potentially dropped from the intervention due to: 1) adherence to yoga or assessment visits, 2) being deemed unsafe to continue the yoga intervention, 3) worsening of depressive symptoms, or 4) suicide risk.

Please see section 8 (Intervention Discontinuation) for operational definitions of the above.

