5.2 Handling of Study Interventions

The infrastructure of the MGH DCRP will permit blinded MD and PhD-level clinician assessors or psychology interns (under supervision by a licensed clinical psychologist) at no additional cost to the study. Any unblinded assessors (MD and PhD- level staff or psychology interns designated prior to the start of the study) will not have access to data nor involvement in data monitoring or analyses. All psychology interns are closely supervised by MD and PhD-level staff, and are trained in the administration and rating of depression diagnostic scales.

Blinded DCRP assessors will perform primary and secondary endpoint collection. The research assistant welcoming the subject will remind the subject not to unblind the blinded assessors at each assessment visit. The research assistant will not be blinded, as they will be collecting attendance data from the yoga studios. If assessment visits are conducted by phone (on an as needed basis to reduce subject burden), blinded assessors will remind participants not to unblind them at the beginning of the call.

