9.5 Outcomes

The blinded assessors will collect the primary outcome of interest, IDS-CR. The Advisory Committee and DSMB will be unblinded.

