9.5.1 Primary Outcome

Primary Outcome Measures

Acceptability Interview (primary aim I): A 19-question qualitative interview assesses perception of ease of participation, program likeability, and perceived benefits of the yoga program. Adapted from DeBoer et al.³⁴.

Inventory of Depressive Symptomatology (IDS-CR): A valid and reliable 30-item measure that is designed to assess severity of depression. The questions focus on neurovegetative and other depressive symptoms experienced over the past seven days. Higher scores indicate more severe pathology. A decrease of 50% or more in the IDS-CR score is considered to be a positive response to treatment, while a final score of 11 or less is considered typical remission.

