10. DATA COLLECTION AND QUALITY ASSURANCE

10.1 Data Collection Forms

Data will be collected on the specified CRFs. The Research Coordinator will be responsible for collecting all self-report and other non-doctoral level staff CRFs. We will designate a blinded Coordinator (not the primary Research Coordinator for the study) to manage the assessment data vis-a-vis quality checking, entering it in the database, and assisting with analysis, as needed. Doctoral level staff conducting clinician-ratings and/or medical assessments will be responsible for completing the appropriate CRFs. Blinded assessors will complete an IDS-CR, the primary study endpoint. All forms will have a participant ID with no other identifying information, as specified in section 11.3 below.

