10.2 Data Management

Self-report data provided by study subjects will be reviewed by blinded study staff for completeness and quality (such as multiple answers when one response is allowed) and all attempts will be made to solve problems prior to the subject leaving the premises. Any incomplete data, illegible, or questionable data provided by blinded assessors will be resolved through feedback with the clinician, within one day following the study visit. This study will utilize REDCap (Research Electronic Data Capture), a browser-based, metadata-driven EDC software solution and workflow methodology for designing clinical and translational research databases. REDCap is secured with password protection. Individual subjects' information will be entered into the database using study ID numbers. No personal identifiers will be stored.

The REDcap system will flag any remaining data quality problems (such as data values outside the expected range) during data entry; any problems will be resolved before the record is added to the database. Extensive quality control procedures for handling and assaying laboratory samples will be carried out to ensure complete and valid biological data. Early in the study and periodically throughout the period of data collection, data will be reviewed by the study Statistician for completeness, consistency, and other indicators of data quality in a

blinded fashion. Missing data will be described but will be inexplicitly imputed in all analyses by using only available data. All primary endpoint data will be quality-assured and assessed by blinded raters. Any errors in completion will be reviewed to determine if directions or procedures need to be altered. In this case, permission from the IRB will be requested to change any procedure. If it is determined that patients are misinterpreting any instrument and answering incorrectly as a result, they will be given proper clarification and instruction.

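### At Visit 6 only the immediate yoga group has the Acceptability Interview, so the rule that blinded assessors collect all primary endpoints cannot be kept there with the blind intact

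*Combined protocol and SAP*

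**What the plan says.** **Who collects endpoints.** Section 5.2: "Blinded DCRP assessors will perform primary and secondary endpoint collection". Section 6.2.3 is broader: "Blinded assessors will complete all primary and secondary endpoint collection". Two other places are narrower. Section 9.5: "The blinded assessors will collect the primary outcome of interest, IDS-CR". Section 10.1: "Blinded assessors will complete an IDS-CR, the primary study endpoint".

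**What the interview is.** Section 9.5.1 places it first among the primary outcome measures and describes it in these terms: "Acceptability Interview (primary aim I): A 19-question qualitative interview assesses perception of ease of participation, program likeability, and perceived benefits of the yoga program".

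**When it is given.** Section 6.2.5 heads the visit "Visit 6: Study Primary Endpoint (Week-8) for IYG and DYG" and lists IDS-CR, HAM-D-28 and the interview, with the qualifier "Acceptability Interview (completed at Visit 11 for DYG". The schedules in 6.1.1 and 6.1.2 agree: the IYG row is marked at Visit 6, the DYG row at Visit 11 only.

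**How the blind is protected.** Sections 5.2 and 6.2.3 have the research assistant remind participants not to reveal their arm; in phone visits the assessor gives the reminder. Neither section says who gives the interview, or when within the visit.

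**The concern.** Participants know their arm (section 9.1) and the control is a waitlist, so blinded rating is the main protection of the IDS-CR and HAM-D-28 against rater expectation. Section 2.2 criticises earlier yoga trials for lacking blinded outcome assessment and says this study was built to answer such criticism. An interview about yoga that only one arm receives at the primary endpoint visit, under a rule that points it to a blinded assessor, works against that aim. A reminder to the participant cannot help a rater whose own task is to ask about the classes.

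Section 9.2 says that the pilot's main purpose is to estimate an effect size for a larger trial. Even modest inflation of that estimate would carry into the next design.

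**Working it through.** The point rests on comparing texts; no figure in the plan decides it.

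1. **Rule.** Under 6.2.3, all primary endpoints are collected by blinded assessors.
2. **Status.** Under 9.5.1, the Acceptability Interview is a primary outcome measure. Steps 1 and 2 together assign it to a blinded assessor.
3. **Timing.** Under 6.1.1, 6.1.2 and 6.2.5, it is given at Visit 6 in the IYG and not in the DYG. Its content is the yoga programme.
4. **Consequence.** Whoever gives it at Visit 6 knows the participant is in the IYG. The rule cannot be met literally with that assessor still blind.
5. **Is the interviewer also the IDS-CR rater?** The plan does not say so and does not rule it out.
6. **Does the interview come before the ratings?** The Visit 6 list puts IDS-CR and HAM-D-28 before the interview and the MINI Mood Module after it, but nothing makes the list an order of administration. The note at the end of 6.2.4 lets visits be split into two occasions with clinician ratings by phone, so the ratings could follow the interview.
7. **After the visit.** Under 10.2, incomplete, illegible or questionable assessor data "will be resolved through feedback with the clinician, within one day following the study visit", which could fall after the interview. At the IYG 1-month visit (Visit 7), nothing stops an interviewer from Visit 6 from rating the IDS-CR and HAM-D-28.

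**Scale of a possible bias (illustration).** The documents give no estimate of how far knowledge of the arm shifts a rating. The test is the one in section 9.2: a two-sided t-test at .05 with n = 32 per arm, 2n − 2 = 62 degrees of freedom and noncentrality d × √(n/2) = d × √16 = 4d.

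- Plan's figures first: d = .70 gives 4 × .70 = 2.80 and power 78.7% (stated 79%); d = .50 gives 2.00 and 50.4% (stated 50%). Both reproduce.
- Next, put an assumed between-arm rating shift b in place of d, with no true effect:

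| Assumed b (SD) | Noncentrality, 32 per arm | Rejection rate, 32 per arm | Rejection rate, 40 per arm |
|---|---|---|---|
| 0 | 0 | 5% | 5% |
| 0.1 | 0.4 | 6.8% | 7.3% |
| 0.2 | 0.8 | 12.4% | 14.3% |
| 0.3 | 1.2 | 21.9% | 26.3% |

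These rates treat efficacy as one week-8 contrast. Section 9.6 tests a time-by-condition interaction in a mixed model over several visits, so they do not carry over one to one.

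**The case against.** The strongest reply is that 6.2.3 is loosely worded and was never meant to cover the interview. The listed secondary outcomes include self-report questionnaires, and section 10.1 gives self-report forms to the Research Coordinator, so *all* cannot be literal. Where the plan names what blinded assessors collect (9.5 and 10.1), it names the IDS-CR. Section 5.2 also foresees unblinded assessors, who could give the interview.

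Much of this stands. It shows that the literal reading is probably not the intended one. It does not close the gap: if the rule does not govern the interview, then no one is assigned to it, and 5.2 gives the unblinded assessors no tasks. Either reading needs an edit.

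Two stronger inferences are tempting, and the documents support neither:

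- **That the plan unblinds the IDS-CR rater at week 8.** This needs one person to do both tasks and, for the week-8 score to be affected, needs that person to learn the arm before the rating is final. The plan states neither. The data-query step in 10.2 is general form cleaning and does not speak of re-rating.
- **That assessor blinding is the only blinding in the trial.** The biostatistician is blinded and the PI has no data access until database lock (6.2.3), and a blinded coordinator checks and enters assessment data (10.1). Those measures do not protect the rating itself, but they exist.

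The 1-month exposure weighs less than the week-8 one. Secondary Aim II is exploratory and compares participants with their own week-8 values, and the primary analyses use pre-crossover data only (9.3, 9.6).

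**Conclusion.** The point holds as an internal conflict and an unassigned task. Read together, 5.2, 6.2.3 and 9.5.1 direct a blinded assessor to give, at the week-8 primary endpoint visit, an interview that reveals the arm. The blind of the IDS-CR and HAM-D-28 rater is at risk at Visit 6 if the same person does both and the interview comes first or the visit is split. It is also at risk at the IYG 1-month visit if that person rates again.

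The size of any bias is unknown. The rejection rates shown depend wholly on an assumed shift and on the premise that the same person both interviews and rates. They show why a cheap safeguard is worth having and do not estimate harm. This is a low-cost improvement to make before the text is relied on, not evidence that the week-8 result is biased.

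**What to change.** - In 5.2 and 6.2.3, limit the blinded-assessor rule to the clinician-rated scales (IDS-CR, HAM-D-28, MINI Mood Module, C-SSRS). This agrees with 9.5 and 10.1.
- In 6.2.5, assign the Acceptability Interview to existing unblinded staff who do not rate that participant. Examples are the research assistant or the primary Research Coordinator, but not the blinded coordinator of 10.1.
- State that the interview is given only after the Visit 6 clinician ratings are completed and signed, including when the visit is split or the ratings are done by phone.

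**Cost.** A few sentences of protocol text and a fixed order within Visit 6, which removes some scheduling freedom when a visit is split. No new staff are needed: under 5.2, an unblinded research assistant already welcomes participants at each assessment visit.
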